2. SAMPLE SIZE AND STATISTICAL POWER CONSIDERATION

Sample Size Considerations (Part A and Part B): The sample size calculation for Part B is based on the secondary endpoint of the mean number of days with any IGISIS individual symptom intensity score ≥ 2 .

Assuming the mean number of days with any IGISIS individual symptom intensity score ≥ 2 is 3.5 and 2.0 for the DMF and ALKS 8700 treatment groups, respectively, a sample size of 500, including 60 randomized subjects per group (120 subjects in total) in Part A and 190 randomized subjects per group (380 subjects in total) in Part B, will provide at least 80% power to detect about a 42% reduction in the number of days with any IGISIS individual symptom intensity score ≥ 2 for the ALKS 8700 treatment group relative to the DMF treatment group, at an alpha level of 0.05 (two-sided) using a negative binomial regression approach. The sample size calculation assumes a standard deviation of 5.9 in the number of days with any IGISIS individual symptom intensity score ≥ 2 relative to exposure days for the DMF treatment group in Part A and Part B.

Assuming the mean number of days with any IGISIS individual symptom intensity score ≥ 2 is 3.5 and 2.0 for the DMF and ALKS 8700 treatment groups, respectively, a sample size of 380 randomized subjects (190 subjects per treatment group) in Part B will provide at least 80% power to detect about a 42% reduction in the number of days with any IGISIS individual symptom intensity score ≥ 2 for the ALKS 8700 treatment group relative to the DMF treatment group, at an alpha level of 0.05 (two-sided) using a negative binomial regression approach. The sample size calculation assumes a standard deviation of 5.9 in the number of days with any IGISIS individual symptom intensity score ≥ 2 relative to exposure days for the DMF treatment group in Part B.

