3.3. Demographics and Baseline Characteristics

Summary statistics will be provided for all demographic variables and baseline characteristics by treatment group and overall. Demographic data including age, age category (<40, \geq 40 years), gender, race, weight, body mass index, ethnicity and region (US and non-US) will be summarized by treatment group and overall.

Baseline characteristics will be summarized by treatment group, using descriptive statistics. These include years since disease (multiple sclerosis [MS]) onset, years since MS diagnosis, number of MS relapses in the past 12 months, prior MS treatment, [REDACTED].

Baseline magnetic resonance imaging (MRI) parameters (number of gadolinium-enhancing [GdE] lesions, GdE lesion category [0, 1-4, 5-8, and >8], T2 lesion volume and Normalized Brain Volume [NBV]) will also be summarized by treatment group and overall.

Medical history and number of prior disease modifying treatments (DMTs) will be summarized for the safety population using the number of observations and percentage of subjects reporting each category by treatment group and overall.

Demographic, baseline characteristics, medical history and prior MS treatment history listings will be provided for all subjects.

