Event days will be analyzed by the negative binomial regression model, including treatment as factor and adjusting for study parts (not included in part B only analyses), region (US and non-US), age and Body Mass Index (BMI). Additional covariates may also be included in the model. The logarithmic transformation of exposure days will be included in the model as the “offset”

parameter. If the data are underdispersed, or if the negative binomial regression model does not converge, a Poisson regression model with the same covariates will be used instead of the negative binomial regression model. Dispersion will be evaluated from the Pearson Chi-square statistic. If the ratio of the Pearson Chi-square statistic to the degrees of freedom is ≤ 1 which indicates no overdispersion, then a Poisson regression model with adjustment for underdispersion will be used. Count distributions in which the number of intervals with zero events is higher than predicted by a Negative binomial or Poisson model may be modeled using a Zero-inflated model.

This method will also be used for the secondary endpoints by setting the GI symptom intensity score cut off as 1 and 3. Empirical cumulative distribution function plot of number of event days by treatment groups will be presented.

Worst IGISIS symptom intensity score by week during the 5 week treatment period

Worst individual IGISIS symptom intensity score is defined as a subject's worst (i.e., highest) symptom intensity score for any symptom out of all completed IGISIS diaries during a given period. Worst IGISIS symptom intensity scores by week during the 5 week treatment period for each subject will be summarized by treatment groups and will be analyzed using an Analysis of covariance (ANCOVA) model. The model will include treatment as factors, and adjusting for study parts, region (US and non-US), age and BMI. Additional covariates may also be included.

Worst IGISIS individual symptom interference level

Worst IGISIS individual symptom interference level is defined as a subject's worst symptom interference level (No symptom < Not at all < Slightly < Moderately < Quite a bit < Extremely) for a particular symptom out of all completed IGISIS diaries during the treatment period. All five GI symptoms (nausea, vomiting, upper abdominal pain, lower abdominal pain and diarrhea) will be reported separately and summarized by treatment groups.

Sensitivity Analysis of IGISIS Endpoints

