3.6.2.2. Global GI Symptom and Impact Scale

The GGISIS is a global scale to assess the overall intensity, bothersomeness, and functional impact of GI symptoms experienced during the previous 24 hours. This scale will be subject-completed using e-diaries. Subjects will be asked to rate the intensity and bothersomeness of GI symptoms experienced using an 11-point numeric rating scale. Additionally, subjects will be asked to indicate:

- How much their GI symptoms have interfered with their ability to accomplish their regular daily activities using a 5-point Likert scale (not at all, slightly, moderately, quite a bit, extremely),
- Number of hours of work missed due to GI symptoms,
- Impact of GI symptoms on work productivity using a 5-point Likert scale (not at all, slightly, moderately, quite a bit, extremely).

Number of days with a GGISIS symptom intensity score ≥ 2 relative to exposure days

Number of days with a GGISIS symptom intensity score ≥ 2 (event days) is counted among available diaries. Exposure days are the number of days between a subject's first dose date plus one and last dose date during treatment period, inclusive.

Event days will be analyzed by the negative binomial regression model, using treatment as factors and adjusting for study parts (not included in part B only analyses), region (US and non-US), age and BMI. Additional covariates may also be included in the model. The logarithmic transformation of exposure days will be included in the model as the "offset" parameter. If the data are underdispersed, or if the negative binomial regression model does not converge, a Poisson regression model with the same covariates will be used instead of the negative binomial regression model. Dispersion will be evaluated from the Pearson Chi-square statistic. If the ratio of the Pearson Chi-square statistic to the degrees of freedom is ≤ 1 which indicates no overdispersion, then a Poisson regression model with adjustment for underdispersion will be used. Count distributions in which the number of intervals with zero events is higher than predicted by a Negative binomial or Poisson model may be modeled using a Zero-inflated model.

This method will also be used for the secondary endpoints by setting the GI symptom intensity score cut off as 1 and 3. Empirical cumulative distribution function plot of number of event days by treatment groups will be presented.

Worst GGISIS bothersome score and interference level

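### The Poisson fallback for a non-converging negative binomial model carries no variance correction for overdispersion

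*SAP*

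**What the plan says.** SAP 3.6.2.1 analyses event days by negative binomial regression with treatment, study part, region, age and BMI, and log exposure days as offset. It gives two reasons for leaving that model. One is underdispersion. The other follows in the same sentence: "or if the negative binomial regression model does not converge, a Poisson regression model with the same covariates will be used instead". Dispersion is judged from the Pearson chi-square over its degrees of freedom. If that ratio is at most 1, "then a Poisson regression model with adjustment for underdispersion will be used". No action is stated for a ratio above 1 after non-convergence. A zero-inflated model is optional and is tied to an excess of zeros, not to non-convergence.

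The rule extends to the other IGISIS cut-offs: "This method will also be used for the secondary endpoints by setting the GI symptom intensity score cut off as 1 and 3". SAP 3.6.2.2 repeats it for the GGISIS counts: "if the negative binomial regression model does not converge, a Poisson regression model with the same covariates will be used instead". It therefore governs the primary endpoint and the six count-type secondary endpoints.

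SAP Section 2 plans on widely scattered counts. The mean number of event days "is 3.5 and 2.0 for the DMF and ALKS 8700 treatment groups, respectively", and the calculation "assumes a standard deviation of 5.9 in the number of days with any IGISIS individual symptom intensity score" of at least 2 for DMF.

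**The concern.** The two triggers call for different handling. Under underdispersion, a Poisson model with a downward scale adjustment is sensible. Non-convergence says nothing certain about dispersion: the fit may fail because the counts are close to Poisson, or for numerical reasons while the counts are strongly overdispersed. In the second case a Poisson model without a scale parameter or a sandwich variance ignores most of the between-subject variation.

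The p-value from this model decides the superiority claim in 3.6.2.1, which can go in either direction at two-sided 0.05. A fallback is written for the unlikely case and has to be valid there.

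**Working it through.** **Inputs.** From SAP Section 2: means 3.5 (DMF) and 2.0 (ALKS 8700), SD 5.9 for DMF, 250 per group for Parts A and B together, 190 per group for Part B, two-sided alpha 0.05. Assumptions made here: 5.9 is the SD of the day count, and the dispersion parameter k is the same in both arms, since the SAP gives an SD for DMF only.

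**1. The plan's own figure.**
- k = (5.9² − 3.5)/3.5² = 31.31/12.25 = 2.556.
- SE of the log rate ratio = √[(1/3.5 + 1/2.0 + 2k)/n] = √(5.898/n), which is 0.154 at n = 250 and 0.176 at n = 190.
- Power = Φ(|ln(2.0/3.5)|/SE − 1.96) = 95.4% and 88.8%. The stated power of at least 80% is reproduced for both sample sizes.

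**2. Overdispersion in the planning values.** Variance/mean = 34.81/3.5 = 9.95. The unscaled Poisson SE is too small by √9.95 = 3.15.

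**3. Type I error if an unscaled Poisson test is used.** Let φ = 1 + k × mean; the error is then 2 × [1 − Φ(1.96/√φ)].

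| Null mean | φ | √φ | Type I error |
|---|---|---|---|
| 3.5 | 9.95 | 3.15 | 53% |
| 2.75 | 8.03 | 2.83 | 49% |
| 1.0 | 3.56 | 1.89 | 30% |

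Simulation without covariates (20,000 trials per setting, negative binomial counts) gave 53-54% at mean 3.5 and 48-49% at mean 2.75. The Pearson ratio was never 1 or less, so the stated underdispersion adjustment would not have applied.

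**4. The same in terms of the estimate.** At the planned means and 250 per group, the Poisson SE is √[(1/3.5 + 1/2.0)/250] = 0.056, against 0.154. The rate ratio that just reaches p < 0.05 is exp(−1.96 × 0.056) = 0.90 instead of exp(−1.96 × 0.154) = 0.74.

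**5. How often the fallback triggers.** These are simulations under the null with the named covariates only. In the main runs, counts were capped at exposure, there were 250 per arm, fitting was by Newton, and failure meant no convergence, a non-finite SE or a dispersion estimate at zero.
- Mean 2.75, k = 2.56: 0 failures in 2,000 trials.
- Mean 1.0, k = 2.56: 10 in 2,000 (0.5%); a separate run gave 2 in 800 (0.25%).
- Assumed mean 0.4 with k = 6: 14 in 600 (2.3%).
- Truly Poisson counts, mean 2.75: 764 in 1,000.

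In the separate mean 1.0 run and the mean 0.4 run the Poisson model did converge on the failing trials, so the route to an unscaled p-value exists. With truly Poisson counts the unscaled test rejected 4.7% of the time, so there the fallback works as intended.

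**6. Size overall.** The simulated type I error of the whole rule with the named covariates was 5.6% (mean 2.75) and 5.2% (mean 1.0). The 5.6% cannot come from the fallback, which was never used in that setting. As a rough gauge, suppose that failing trials reject at the rate of step 3. At mean 1.0 the excess is 0.005 × (0.30 − 0.05), about 0.1 percentage point. At mean 0.4 with k = 6, φ = 1 + 2.4 = 3.4, the conditional rate is about 29%, and the excess is 0.023 × (0.29 − 0.05), about 0.6 percentage point.

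**The case against.** The strongest reply is that the gap has no visible effect under the model that the SAP names. Step 5 bears this out for the primary endpoint. Non-convergence is mostly a sign of counts close to Poisson, where an unscaled SE is adequate. The programming specifications (Section 8) are a separate document, and the content of the Part A SAP (Appendix I) is not shown; either may set a scale option. All of this stands and limits the weight of the point. It does not supply the missing rule: the SAP spells out a variance adjustment for one branch and is silent on the other.

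A reader might go further. Since "Additional covariates may also be included in the model", a covariate with a very sparse level could make the negative binomial fit fail often, and the overall type I error would then rise well above 5%. The documents do not support this. Race, the obvious candidate, appears in 3.3 only as a demographic variable to be summarised, and no level sizes are given. The mechanism also fails to separate the two models. If every subject in a level has zero event days, that coefficient has no finite estimate in the Poisson model with the same covariates either. In simulations that added race with an assumed 0.5% level, at means 2.75 and 1.0, Newton Poisson converged in only 7% and 12% of the trials where Newton negative binomial had failed. A different optimiser (BFGS) fitted the negative binomial model in about 94-95% of them. Failure rates obtained that way describe the software, not the SAP's rule.

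**Conclusion.** The point holds as a minor one. In 3.6.2.1 and 3.6.2.2 the non-convergence route leads to a Poisson model with no stated protection against overdispersion, although the planning values imply a variance almost ten times the mean. A reader might take the 53%, 49% and 30% as the trial's type I error. They are not: each is conditional on the fallback being used on overdispersed counts. The chance of that is very small for the primary endpoint and about 0.3-2% for rarer-event secondary endpoints, so the expected effect is small.

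The figures rest on k = 2.56 in both arms, on null means of 2.75 and 1.0 and a rare-event setting (mean 0.4, k = 6) that are assumed here, and on Newton fitting for the main failure rates. That the SAP states no correction for this branch does not depend on any of these.

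**What to change.** In both 3.6.2.1 and 3.6.2.2, state that whenever a Poisson model replaces the negative binomial model, for either reason, its standard errors are multiplied by the square root of the Pearson chi-square over degrees of freedom from that Poisson fit. This also defines the underdispersion adjustment that the SAP mentions without specifying. A sandwich variance would serve too, but one method should be named.

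The cost is one sentence per section and one option in the model call. With scaling, simulated type I error was 4.7-5.3% across negative binomial and bounded beta-binomial counts. Power at 190 per group and means 3.5 versus 2.0 was 87.8%, against 88.5% for the negative binomial model (5,000 trials). In the 764 failing trials with truly Poisson counts, the scaled test rejected 5.6%, against 4.7% unscaled.

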3.6.2.2. Global GI Symptom and Impact Scale

The GGISIS is a global scale to assess the overall intensity, bothersomeness, and functional impact of GI symptoms experienced during the previous 24 hours. This scale will be subject-completed using e-diaries. Subjects will be asked to rate the intensity and bothersomeness of GI symptoms experienced using an 11-point numeric rating scale. Additionally, subjects will be asked to indicate:

- How much their GI symptoms have interfered with their ability to accomplish their regular daily activities using a 5-point Likert scale (not at all, slightly, moderately, quite a bit, extremely),
- Number of hours of work missed due to GI symptoms,
- Impact of GI symptoms on work productivity using a 5-point Likert scale (not at all, slightly, moderately, quite a bit, extremely).

Number of days with a GGISIS symptom intensity score ≥ 2 relative to exposure days

Number of days with a GGISIS symptom intensity score ≥ 2 (event days) is counted among available diaries. Exposure days are the number of days between a subject's first dose date plus one and last dose date during treatment period, inclusive.

Event days will be analyzed by the negative binomial regression model, using treatment as factors and adjusting for study parts (not included in part B only analyses), region (US and non-US), age and BMI. Additional covariates may also be included in the model. The logarithmic transformation of exposure days will be included in the model as the "offset" parameter. If the data are underdispersed, or if the negative binomial regression model does not converge, a Poisson regression model with the same covariates will be used instead of the negative binomial regression model. Dispersion will be evaluated from the Pearson Chi-square statistic. If the ratio of the Pearson Chi-square statistic to the degrees of freedom is ≤ 1 which indicates no overdispersion, then a Poisson regression model with adjustment for underdispersion will be used. Count distributions in which the number of intervals with zero events is higher than predicted by a Negative binomial or Poisson model may be modeled using a Zero-inflated model.

This method will also be used for the secondary endpoints by setting the GI symptom intensity score cut off as 1 and 3. Empirical cumulative distribution function plot of number of event days by treatment groups will be presented.

Worst GGISIS bothersome score and interference level

Subject's worst GGISIS bothersome score and worst interference level (No Symptom < Not at all < Slightly < Moderately < Quite a bit < Extremely) out of all completed IGISIS diaries during the treatment period will be summarized by treatment groups.

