¹⁴ The IGISIS will be completed twice daily (should be completed within 9 hours after taking each dose of study drug) and the GGISIS will be completed once daily (each morning prior to taking the morning dose of study drug) using e-diaries during the randomized treatment period (Visit 3 to Visit 8).

¹⁵ Use "Screening" version at screening (Visit 1) and "Since-Last-Visit" version for all subsequent time points.

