3. DATA ANALYSIS

3.1. General Statistical Methodology

The safety and efficacy endpoints will be summarized by treatment group and overall as described below. In general, summary statistics (n, mean, standard deviation [SD], median, minimum, and maximum for continuous variables, and number and percentage of subjects in each category for categorical variables) will be provided by treatment group and overall. All summary tables will be based on observed data, and missing values will not be imputed unless otherwise indicated. Measurements collected from unscheduled visits or repeated assessments will not be included in the by-visit summary tables or figures, but will be included in the analyses for the potentially clinically significant (PCS) post-baseline values and subject listings. Source data for the summary tables and statistical analyses will be presented as by-subject data listings.

Baseline value is defined as the last non-missing assessment prior to the first dose of study drug.

All statistical tests and confidence intervals (CIs), unless stated otherwise, will be 2-sided and will be set at an alpha level of 0.05.

All the efficacy analyses will be summarized by the planned treatment assignment, and all the safety analyses will be summarized by actual treatment.

The data will be summarized for the following two study periods as appropriate.

- Treatment Period, which is defined as the period between the first dose date after randomization and the last dose date plus 1 day, inclusive.
- Follow-up Period, which is defined as the period between the date of the last dose date plus 2 day and the last study date, inclusive.

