3.6.2.1. Individual GI Symptom and Impact Scale

The IGISIS is designed to assess the incidence, intensity, onset, duration, and functional impact of 5 individual GI symptoms: nausea, vomiting, upper abdominal pain, lower abdominal pain, and diarrhea. This scale will be subject-completed using e-diaries. These 5 symptoms were included in the IGISIS as they were the most commonly reported GI symptoms in the Tecfidera® Phase 3 placebo-controlled trials. Subjects will be asked to rate the severity of each individual symptom via an 11-point numeric rating scale ranging from 0 (did not have) to 10 (extreme). Subjects will also be asked to indicate the start and stop times of each GI symptom. Additionally, subjects will be asked to indicate how much each symptom has interfered with their ability to accomplish their regular daily activities using a 5-point Likert scale (not at all, slightly, moderately, quite a bit, extremely).

GI tolerability assessment utilizing the IGISIS will focus on intensity scores (11 point numeric severity rating scale) of each individual symptom. If an IGISIS symptom is recorded as ongoing, only the initial intensity score will be collected (i.e., logically skipped item) and the initial intensity score collected at the symptom start will be carried over until symptom end.

Number of days with any IGISIS individual symptom intensity score ≥ 2 relative to exposure days

Number of days with any IGISIS individual symptom intensity score ≥ 2 (event days) is counted among observed diaries. Exposure days are the number of days between a subject's first dose date and last dose date during treatment period, inclusive.

Let $\theta^{(1)}$ and $\theta^{(2)}$ denote the mean number of days with any IGISIS individual symptom intensity scores ≥ 2 , for ALKS 8700 and DMF, respectively. Comparison of GI tolerability will be tested at 5% level of significance in a two-sided test, through the following hypothesis of no treatment effect:

$$H_0: \theta^{(1)} = \theta^{(2)} \quad \text{vs. } H_a: \theta^{(1)} \neq \theta^{(2)}$$

ALKS 8700 will be *claimed superior* to DMF if *the estimated $\theta^{(1)}$ is less than the estimated $\theta^{(2)}$ and p-value is less than 0.05 (in a 2-sided test)*. DMF will be *claimed superior* to ALKS 8700 if *the estimated $\theta^{(2)}$ is less than the estimated $\theta^{(1)}$ and p-value is less than 0.05 (in a 2-sided test)*.

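### GGISIS exposure stops one day short of the diary for the last dosing day, so a subject dosed on a single date has zero exposure and an undefined offset in three secondary models

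*SAP*

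**What the plan says.** SAP section 3.6.2.2 defines the GGISIS denominator as the number of days between a subject's "first dose date plus one and last dose date during treatment period, inclusive". Section 3.6.2.1 defines the IGISIS denominator without the shift: "Exposure days are the number of days between a subject's first dose date and last dose date during treatment period, inclusive".

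The two scales differ in timing. The GGISIS covers "GI symptoms experienced during the previous 24 hours" (section 3.6.2.2). Under Table 1, footnote 14, "the GGISIS will be completed once daily (each morning prior to taking the morning dose of study drug").

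The GGISIS numerator has no start or end date. The text says only that the number of days at or above the cut-off ("event days) is counted among available diaries". On the offset it says: "The logarithmic transformation of exposure days will be included in the model". No rule is given for exposure of zero.

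Two other definitions matter. Section 3.1 defines the Treatment Period as "the period between the first dose date after randomization and the last dose date plus 1 day, inclusive". Section 3.2.1.2 admits to the full analysis set anyone with one dose and one post-baseline entry on either scale.

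**The concern.** A GGISIS diary completed on the morning of day t reports mainly on day t − 1. The diary on the first dosing day therefore describes time before treatment, and starting at first dose date + 1 is right. By the same reasoning, symptoms on the last dosing day are reported on last dose date + 1. The SAP moved one end of the window and not the other, although its own Treatment Period reaches that extra day.

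There are two consequences. First, the exposure formula returns zero for a subject whose first and last dose share a date, and the model cannot use that subject. Second, the numerator is left open. Two programmers could both follow section 3.6.2.2 and obtain different event counts, depending on whether they admit the diary from the day after last dose. Three secondary endpoints are involved: days with GGISIS intensity ≥1, ≥2 and ≥3.

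**Working it through.** The SAP gives no figure on this point to reproduce. The check is date arithmetic, followed by a simulation for size.

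**Lengths.** Let D = last dose date − first dose date + 1.
- IGISIS exposure (section 3.6.2.1): D.
- GGISIS exposure (section 3.6.2.2): last − (first + 1) + 1 = D − 1.
- Morning diaries that report on-drug days: first + 1 to last + 1, which is D diaries.

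**If the diary on last dose date + 1 is counted,** up to D event days are set against D − 1 exposure days, and the rate is overstated by up to D/(D − 1):

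| D | GGISIS exposure | On-drug diaries | Factor |
|---|---|---|---|
| 1 | 0 | 1 | undefined |
| 2 | 1 | 2 | 2/1 = 2.00 |
| 5 | 4 | 5 | 5/4 = 1.25 |
| 14 | 13 | 14 | 14/13 = 1.077 |
| 35 | 34 | 35 | 35/34 = 1.029 |

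**If that diary is not counted,** numerator and denominator both span D − 1 days and the factor is 1. The last dosing day then contributes nothing.

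**Under both readings,** D = 1 gives log(0). The same subject has IGISIS exposure 1 and log(1) = 0, so stays in the IGISIS models.

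**Size for the comparison.** The simulation used the first reading (diary counted) and a true rate ratio of 1. It had 250 subjects per arm and a negative binomial model without covariates. All of the following are assumptions, since the SAP gives no early-stop or GGISIS event rates: 0.1 event days per day, dispersion 2.5, early stops spread evenly over days 1 to 14, and 35 days for everyone else. The rate ratio is the arm with more early stops over the other.

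| Early stops by arm | Ratio with offset log(D) | Ratio with offset log(D − 1) | Shift | Subjects lost of 500 |
|---|---|---|---|---|
| 2% vs 6% | 0.991 | 0.995 | 0.9946/0.9912 = 1.003 | about 1.4 |
| 5% vs 15% | 0.993 | 1.002 | 1.0018/0.9925 = 1.009 | about 3.6 |

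Both offsets were applied to the same simulated trials, so the shift between the columns is what counts. The losses agree with direct arithmetic: 250 × (0.02 + 0.06)/14 = 1.4 and 250 × (0.05 + 0.15)/14 = 3.6.

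**With the window ended at last dose date + 1,** exposure is D, the factor is 1 for every D, and a one-date subject has log(1) = 0.

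**The case against.** The best defence is that the window is coherent as written. After the first dosing day, diaries taken before a morning dose run from first dose date + 1 to last dose date. That is D − 1 diaries against D − 1 days, and the changed start shows that the author adapted the window to this scale. If event days are counted over the same dates, there is no inflation. This stands in part. A reader might infer that the definition inflates GGISIS rates in early stoppers as a matter of fact. The SAP does not support that, because it never says whether the extra diary is counted. Where it is counted, every subject is affected, not only early stoppers. But the defence leaves the last dosing day unreported and does nothing for one-date subjects.

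A second objection concerns the remedy. GGISIS collection is scheduled only from Visit 3 to Visit 8, and completers may move to open-label ALKS 8700 in the extension study. If the last dose falls on the Visit 8 date, an unconditional extension would add an exposure day with no scheduled diary, or a day belonging to the next study. This stands, and the fix needs a cap.

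Third, dataset and programming specifications are separate documents (sections 6 and 8) and may set the numerator window or a zero-exposure rule. That could settle the open numerator. It would not settle the denominator, which the SAP states outright: a specification that follows it returns zero.

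Last, one might infer that the subjects most intolerant of treatment are lost to the trial. The SAP has no data on who stops on the first day. Such subjects remain eligible for the IGISIS primary analysis and are included in the safety summaries.

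**Conclusion.** The point holds as a defect in the stated derivation. Two parts need no assumption: the window omits the diary that reports the last dosing day, and the offset is undefined for a full-analysis-set subject dosed on a single date. The rate overstatement of up to D/(D − 1) is conditional on counting the diary from the day after last dose. The alternative is loss of that day's symptoms.

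The expected effect is small. For completers the factor is about 1.03 in both arms and largely cancels in a rate ratio, so the comparison is biased only if early stopping differs by arm. Under the assumed shares the rate ratio shifts by less than 1% and about 1 to 4 of 500 subjects are lost. Other shares would give other figures. Nothing here supports a claim of material bias in the GGISIS results, and the IGISIS primary endpoint is not affected. The reason to act is that the rule fails for some subjects under either reading and is cheap to correct.

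**What to change.** In section 3.6.2.2, give GGISIS event days and exposure days one window: first dose date + 1 through last dose date + 1. End it no later than the end of GGISIS collection at Visit 8 and before any first dose in the extension study. Set a minimum exposure of 1 day for any subject with a post-dose GGISIS diary. Apply the same window to all three cut-offs.

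The cost is a short change of SAP wording and a revised derivation, with no change to data collection. The downside is that some subjects may still carry a denominator day without a diary, for example if no entry was made on the morning after the last dose.

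### The worst-GGISIS summary names the wrong diary and, separately, does not exclude the Day 1 GGISIS completed before the first dose

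*SAP*

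**What the plan says.** - **Source and window of the summary.** Section 3.6.2.2, under the sub-heading on worst GGISIS bothersomeness and interference, takes the worst values "out of all completed IGISIS diaries during the treatment period will be summarized by treatment groups".
- **What the GGISIS asks.** The same section states: "Subjects will be asked to rate the intensity and bothersomeness of GI symptoms experienced using an 11-point numeric rating scale". It also gives the GGISIS one overall interference question, and has it assess the "functional impact of GI symptoms experienced during the previous 24 hours".
- **What the IGISIS asks.** Section 3.6.2.1: "The IGISIS is designed to assess the incidence, intensity, onset, duration, and functional impact of 5 individual GI symptoms". Interference is asked for each symptom, and no bothersomeness item is described.
- **When the GGISIS is completed.** Table 1, footnote 14 (Section 1.2): "the GGISIS will be completed once daily (each morning prior to taking the morning dose of study drug". This applies from Visit 3 to Visit 8.
- **Treatment period.** Section 3.1 defines it as "the period between the first dose date after randomization and the last dose date plus 1 day, inclusive".
- **Baseline.** Section 3.1 uses the most recent value recorded before first dosing.
- **GGISIS exposure days.** Section 3.6.2.2 counts them between the "first dose date plus one and last dose date during treatment period, inclusive". The event days themselves come from whatever diaries are available, with no start date given.

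**The concern.** The sentence cannot be programmed as it stands. No bothersome score can be read from a diary without that item. Interference exists on both instruments, so a literal reading could return a per-symptom IGISIS answer in place of the overall GGISIS answer.

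Correcting the diary name leaves a second question, about dates. The treatment period is defined by calendar date and includes the day of first dose. The GGISIS that morning is filled in before dosing and looks back, so it says nothing about study drug. A maximum is fixed by a single record. A subject whose highest score is on that diary would therefore be tabulated with a pre-drug level as the worst level under treatment.

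**Working it through.** The plan gives no figure to reproduce here, so the check compares the definitions and counts dates.

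**Diary name**

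| Item | GGISIS (3.6.2.2) | IGISIS (3.6.2.1) |
|---|---|---|
| Bothersomeness | yes | not described |
| Interference | one overall question | one per symptom |

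The IGISIS interference endpoint in Section 3.6.2.1 uses almost the same phrase, "for a particular symptom out of all completed IGISIS diaries during the treatment period", and there it is correct. The GGISIS sentence is probably a carry-over from it.

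**Window, with the source read as GGISIS**

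Let Day 1 be the first dose date and L the day of the last dose. Assume one GGISIS each morning, completed as footnote 14 schedules.

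1. The treatment period covers Days 1 to L + 1, so it holds up to L + 1 diaries.
2. The Day 1 diary is completed before any dose and recalls the preceding 24 hours, so it covers only pre-drug time.
3. Diaries on Days 2 to L + 1 can reflect study drug. That leaves L diaries.
4. The share of eligible diaries that is wholly pre-drug is 1 / (L + 1).

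| Last dose | Diaries in window | Wholly pre-drug | Share | Diaries if the window starts on Day 2 |
|---|---|---|---|---|
| Day 35 | 36 | 1 | 1/36 = 2.8% | 35 |
| Day 7 | 8 | 1 | 1/8 = 12.5% | 7 |
| Day 1 | 2 | 1 | 1/2 = 50% | 1 |

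These are shares of diaries, not of subjects. A subject's result changes only if the Day 1 score exceeds every later score.

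**Comparison with the event-day endpoint**

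GGISIS exposure days run from Day 2 to Day L, which is L − 1 days (34 when L = 35). That count enters the model as the offset. It does not say which diaries may supply event days, so the Day 1 diary is not expressly excluded there either.

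**The case against.** The strongest reply is that this is a slip with little practical risk. The sub-heading and the opening of the sentence both say GGISIS, and a bothersome score cannot be drawn from the IGISIS, so only interference is open to misreading. The status of the Day 1 diary is also less settled than the window suggests. Footnote 13 covers GGISIS diaries in the lead-in week before randomization, and a diary completed on the morning of Visit 3 could fall under it. A programmer could reasonably flag that record as baseline. Dataset and programming specifications are separate documents (Sections 6 and 8) and may settle the matter. All of this is fair. What stands is that the SAP sentence is wrong as written and that nothing in the SAP removes the Day 1 diary.

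A reader might also infer stronger claims that the document does not support:

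- **That the wrong diary lets pre-treatment symptoms in.** It does not. On-treatment IGISIS diaries are scheduled after each dose. The pre-drug record enters only through the date window, once the source is read as GGISIS.
- **That the SAP already excludes Day 1 from event days and so contradicts itself.** The later start date is stated for exposure days only.
- **That a given share of subjects is affected, or that the arms are pulled together.** The SAP gives no distribution of scores from which either could be calculated.

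**Conclusion.** Both defects are present in the text, and they are independent of each other. The diary name is a plain wording error. The window is an omission: as written, a diary that covers only pre-drug time can be both the baseline and the worst on-treatment value.

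The importance is minor. These scores are not among the primary or secondary endpoints listed in Section 3.6.2. They are summarized by arm with no test or model, and no superiority claim rests on them. The pre-drug diary is 1 of up to 36 for a 35-day completer and weighs more for early stoppers (1 of 8 with last dose on Day 7). The number of subjects whose worst score would change cannot be derived from the SAP.

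The window point assumes that the Day 1 GGISIS is completed before the first dose, as scheduled, and that no separate specification already removes it.

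**What to change.** Replace the sentence in Section 3.6.2.2 with wording such as:

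> Worst GGISIS bothersome score and worst GGISIS interference level out of all completed GGISIS diaries dated from first dose date + 1 to last dose date + 1. The GGISIS completed before the first dose on Day 1 is used as baseline only.

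Two things should be stated with it:

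- **End date.** Last dose date + 1 keeps the diary that reports on the last dosing day and stays inside the treatment period of Section 3.1. It is one day later than the end of the GGISIS exposure days, and the SAP should say so.
- **Event-day count.** State explicitly that the pre-dose Day 1 diary is also excluded from the GGISIS event-day count, for which the SAP now gives no start date.

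The cost is one rewritten sentence, one added line for the event-day count, and a date condition in each derivation. No new data are needed. The remaining drawback is the one-day difference at the end of the two windows, which has to be documented.
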